**TITLE: Visualization of the papilla through use of the NuView device in patients with FAP**

**Protocol Version Date: May 5, 2022**

## 1. PURPOSE

The NuView device is a single-use distal endoscope attachment that is intended to facilitate direct visualization of the papilla with a forward viewing endoscope in order to eliminate the need for passage of the much bulkier, non-intuitive, risk prone side-viewing endoscope to visualize the papilla. In this early feasibility study, the NuView device will be used to atraumatically insert and navigate a conventional forward-viewing upper endoscope (gastroscope) from insertion at the mouth, through the esophagus, the stomach, and into duodenum to visualize the papilla in patients with familial adenomatous polyposis (FAP). FAP is a hereditary condition in which a person develops numerous precancerous polyps, called adenomas, within the small and large intestine. These patients also have a high prevalence of adenomas that develop on the duodenal papilla, which are particularly hard to visualize due to the curvature and geometry of the small intestine. Currently, it is recommended that FAP patients undergo serial endoscopic exams to assess the colon for polyp formation every year and every 2-3 years to look for adenomas in the small intestine—specifically on the duodenal papilla. This requires two different specialized endoscopes to perform the upper endoscopic procedure. The first endoscope that the endoscopist uses is a forward facing gastroscope, with which they are able to visualize the stomach and portions of the duodenum. Due to the anatomic location of the papilla, the forward-viewing endoscope is not adequate for visualization of the papilla, and therefore the endoscopist must switch to a second specialized endoscope (called a duodenoscope) that allows for side viewing but lacks forward visualization. There are several well-known problems with duodenoscopes. First, they are notoriously difficult to sterilize and have been linked to alarmingly high infections rates that have in some cases resulted in patient deaths. The FDA has even issued a call-to-action to medical device manufacturers to invent new disposable solutions to mitigate or eliminate this problem. Secondly, side-viewing endoscope that are currently used are difficult to navigate because they lack forward viewing capabilities. The NuView device was designed to eliminate the need for a duodenoscope by enabling a forward facing gastroscope to also have some side-viewing capabilities. In this early feasibility study, the NuView device will be used with a forward facing gastroscope to enable FAP patients to undergo their routine screening endoscopic exam. We hypothesize that the minimally invasive endoscopic procedure may offer the following benefits: (1) reduced infection rates due to the elimination of the need for a specialized side-viewing duodenoscope, (2) shorter procedure time including shorter general anesthesia time by eliminating the need to switch endoscopes during the procedure, and (3) yield potentially less trauma to patient tissue due to the atraumatic features of the NuView (only needing to insert and remove one endoscope as compared to using two different endoscopes to complete the examination).

We propose an early feasibility study to determine if visualization of the papilla is possible using a forward facing gastroscope equipped with the NuView. The study will involve only otherwise healthy FAP patients between the age of 18 and 70 (see selection criteria for a full description).

---

J. R. Alexander, R. W. Burt, "High prevalence of adenomatous polyps of the duodenal papilla in familial adenomatous polyposis" *Dig Dis Sci.* 1989;34(2):167-170.

R. M. Humphries and G. McDonnell, "Superbugs on duodenoscopes: The challenge of cleaning and disinfection of reusable devices," *Journal of Clinical Microbiology*, vol. 53, no. 10, pp. 3118, 2015.

United States Senate Health, Education, Labor and Pensions Committee, "Preventable Tragedies: Superbugs and How Ineffective Monitoring of Medical Device Safety Fails Patients," 2016.

FDA, "FDA recommends health care facilities and manufacturers begin transitioning to duodenoscopes with disposable components to reduce risk of patient infection," 2019.

FDA, "The FDA Continues to Remind Facilities of the Importance of Following Duodenoscope Reprocessing

Instructions: FDA Safety Communication,” 2019.

The clinical practice at Vanderbilt University Medical Center is to first perform the routine upper endoscopic exam with a forward-viewing gastroscope to evaluate the patient’s esophagus, stomach, and duodenum. After this has been completed, the forward-viewing endoscope will be removed from the patient and outfitted with the EndoTheia NuView. The endoscope with NuView will then be inserted transorally down the esophagus, traverse the stomach, and be passed into the duodenum for visualization of the papilla. After the papilla is visualized, the endoscope with NuView will be removed from the patient. As per standard of care, the conventional side-viewing endoscope will then be inserted transorally down the esophagus, traverse the stomach, and be passed into the duodenum for visualization of the papilla. The side-viewing endoscope will then be removed from the patient.

[figure not shown]
We plan to enroll 3 FAP patients who are already scheduled to undergo their standard of care endoscopic exam. The primary endpoint of the study is successful visualization of the papilla with the NuView platform.

## 2. DESCRIPTION OF DEVICE

The EndoTheia NuView is a distal endoscope attachment type device which is intended “*to be attached to the distal end of the endoscope to facilitate endoscopic therapy, to be used for the following:*

- *Keeping the suitable depth of endoscope’s view field*
- *Helping the endoscope with being inserted into the gastrointestinal tract”*

The EndoTheia NuView can be seen in Figure 1.

*Figure 1. The NuView device is a distal endoscope attachment device which features (1) an atraumatic tip to help with insertion into the body, (2) a side-viewing surface which enables the physician with more lateral viewing capabilities, and (3) an everting web which interacts with patient tissue to help maintain the correct field of view and increase visualization.*

Distal endoscope attachment devices are not new. There are many such devices currently on the market and in use within the clinical setting. Some similar distal endoscope attachment devices on the market are the Arc Endocuff ([K151801](#)) and the Reveal Distal Attachment Cap ([K140315](#)). These devices function similarly to the NuView device by attaching to the endoscope, maintaining the correct field of view, and helping with atraumatic insertion of the endoscope. The NuView device maintains attachment with the endoscope through a press-fitting attachment that is tight enough to maintain attachment but not tight enough to damage the endoscope in any way, similar to other FDA approved distal attachments. Similarly, the NuView device has an atraumatic insertion tip that is rounded and made from a biocompatible material, which is meant to facilitate atraumatic interaction with the patient's tissue and enable safe insertion of the endoscope into the patient. Another aspect of the NuView device is that it contains soft, flexible side projections to smooth out the mucosal folds inside the gastrointestinal (GI) tract (similar to other FDA approved distal endoscope attachment devices such as the EndoCuff Vision® (Olympus America, PA, USA) and the EndoRings™ (ENDO-AID inc., PA, USA), as well as a side-viewing reflective surface that will redirect a portion of the field of view of the endoscope. The soft projections are proximally-biased, allowing them to fold down onto the endoscope body during insertion, and evert upon retraction to expand and flatten mucosal folds, thereby providing an enhanced view of the lumen as viewed through the side-viewing reflective surface. These features are meant to help keep a suitable depth of the endoscope's view field and to give the surgeon an excellent view of the mucosal lining to visualize tissue to the side of the endoscope, in addition to preserving a portion of the normal forward-facing field of view capabilities. The shape of the NuView device, the flexible side projections, and the side viewing reflective surface will aid in keeping the suitable depth of endoscope's field of view and increase the surgeon's ability to visualize desired tissue targets by smoothing mucosal folds and preventing tissue from collapsing around the endoscope.

**The devices used in this study are the following:**

- I. Olympus Gastroscope GIF-H190 which is FDA cleared for endoscopy and endoscopic surgery within the upper digestive tract.
- II. NuView consisting of a soft distal endoscope attachment device (investigational device).
- III. Olympus Duodenoscope TJF-Q180V which is FDA cleared for endoscopy and endoscopic surgery within the duodenum.

*Table 1. Devices used in this study*

Product	Model	FDA Information	Availability
Olympus Gastrointestinal Videoscope	GIF-H190	K112680	FDA cleared and commercially available
NuView Device	Not available	Investigational	Not commercially available
Olympus Video Duodenoscope	TJF-Q180V	K143153	FDA cleared and commercially available

### 3. PROTOCOL

#### 3.1.1 Synopsis

**Investigational Device:** NuView

**Study Title:** Visualization of the papilla through use of the NuView device in FAP patients.

**Study Design:** Early Feasibility Study

**Number of Participants:** 3

**Study Population:** Adult FAP patients who are already scheduled for their standard of care upper endoscopic FAP screening examination.

**Study Duration:** Upper endoscopic examinations for FAP are relatively short duration outpatient procedures lasting 20-30 minutes in duration. As is standard of care at VUMC, a post-procedure follow-up phone call is then conducted 3-5 days post-procedure.

**Schedule:** (1) Screening of patients for meeting inclusion criteria; (2) Routine upper endoscopic examination with forward-viewing endoscope; (3) Passage of the forward-viewing endoscope with NuView; (4) Passage of the conventional side-viewing endoscope; (5) Follow-up phone call 3-5 days post examination as per VUMC standard practice for patients who have undergone endoscopy.

### 3.1.2 Study Objective

**The objective of this early feasibility study is to** determine if visualization of the papilla is possible using a forward-facing endoscope outfitted with the NuView device.

### 3.1.3 Study Design

#### 3.1.3.1 Overview

This early feasibility study will be a prospective clinical trial in which 3 patients will be enrolled. All patients will undergo their routine yearly upper endoscopic examination using the conventional forward-viewing gastroscope, side-viewing gastroscope, and forward-viewing gastroscope equipped with the NuView platform.

#### 3.1.3.2 Study Endpoints

##### PRIMARY

The primary study endpoint will be successful visualization of the papilla with a standard gastroscope equipped with the NuView platform.

##### SECONDARY

- i. Time of procedure as recorded by research personnel
- ii. Ease of use of the device as recorded by the endoscopist via the completion of a NASA task load index questionnaire post-procedure

### **3.1.4 Study Devices**

The NuView is an investigational distal endoscope attachment type device that consists of soft, flexible, and biocompatible 3D printed material, an embedded optical mirror, and biocompatible adhesive. All materials used in the NuView have both been confirmed to be biocompatible and have been shown to withstand autoclave sterilization well. For all biocompatibility and sterility verification testing information please refer to [Appendix B](#).

### **3.1.5 Participant Selection**

#### **3.1.5.1 Inclusion Criteria**

1. Male or female, 18 to 70 years of age.
2. Able to provide written informed consent.
3. Have FAP

#### **3.1.5.2 Exclusion Criteria**

1. Females who are pregnant. As part of routine pre-operative care, all females of childbearing potential will undergo either urine or blood pregnancy testing.
2. Cancer positive subjects or any patients currently undergoing any treatment or therapy to treat, cure, or mitigate cancer.
3. Patients who do not meet inclusion criteria
4. Patients who are unable or unwilling to provide informed consent

### **3.1.6 Study Procedures**

#### **3.1.6.1 Screening**

Potential subjects will be identified from the list of patients in the Vanderbilt University Medical Center Digestive Disease Center who are scheduled to undergo their endoscopic screening for FAP by members of the VUMC clinical research trained personnel team. Those participants who express interest in taking part in the research study will be asked to sign a written informed consent that has been approved by the Vanderbilt University Medical Center IRB. Participants will have the study explained to them and will be given the opportunity to read and review the consent document and have any questions addressed. Once informed consent is obtained, final eligibility for enrollment into the study will be determined based on the inclusion/exclusion criteria.

Participants will undergo pre-operative and post-operative procedures as per routine standard of care for their VUMC endoscopic exam. We anticipate enrolling 3 patients to complete the study.

#### **3.1.6.2 Day of Endoscopy**

Once the patient has been successfully prepared for the endoscopic procedure and has been administered monitored anesthesia care (MAC) by the VUMC Anesthesia team as per routine care, the following steps will be followed.

*Note: only step “b)” below deviates from the current standard clinical practice for upper endoscopic examination of FAP patients. Step “b)” is when the investigational Non-Significant Risk (NSR) device is used and the only step that is not usually performed during FAP endoscopic*

### ***examinations.***

**a) *Endoscopic assessment using a standard gastroscope.*** This assessment is the first step in the routine FAP patient endoscopic examination. During this step, the endoscopist introduces a gastroscope into the patient to assess the esophagus, stomach, and duodenum for polyps. This will be performed per standard of care without deviation from standard of care procedure.

**b) *Endoscopic visualization of the papilla using a gastroscope equipped with the NuView.*** After the gastroscope assessment is complete and the gastroscope is removed from the patient, the NuView device will be attached to the gastroscope, introduced into the patient, and the papilla will be visualized. Steps in sequential order are:

1. The NuView device's sterile packaging will be inspected and confirmed intact
2. The NuView package will be opened
3. The NuView will then be pressed onto the distal end of the gastroscope using the press-fitting attachment feature and confirmed to be securely fastened
4. The gastroscope equipped with the NuView will be inserted into the patient
5. The gastroscope will be navigated to the duodenum and the papilla will be visualized using the NuView
6. The gastroscope equipped with a NuView will be removed from the patient.

**c) *Duodenoscope visualization of the papilla as a secondary confirmation using another clinically accepted method.*** Following papilla visualization using the NuView, the papilla will be visualized and inspected again using a duodenoscope. This will be performed in the standard method, using the standard protocol for FAP patients during their routine screening upper endoscopic examination. The endoscopist will insert a duodenoscope into the patient and navigate to the duodenum as is normal with routine endoscopic procedures for patients with FAP. Using this accepted clinical method, they will inspect the papilla to confirm what was visualized using the NuView device. This is a protection in line with what is outlined in 21 CFR 812, which states that any diagnostic NSR device should have a confirmation of diagnosis using a second clinically accepted method. Once the papilla has been visualized using the duodenoscope, the duodenoscope will be removed from the patient in the standard clinical method.

**d) *Any adverse events occurring during the surgical procedure will be documented.*** Any adverse events that occur during the procedure will be documented and reported in accordance with 21 CFR 812 and Vanderbilt's IRB protocols.

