### **3.1.6.3 Post-operative visit/follow up**

In line with standard clinical practice for patients who have received MAC at VUMC, the patient is observed for 30 mins during the immediate post-operative period and then released to a chaperone to leave the endoscopy unit. The patient then receives a post-operative phone call 3-5 days post procedure to inquire about status of the patient.

Primary Endpoint: Successful visualization of the papilla with a standard gastroscope equipped with NuView.

Secondary Endpoints:

- i. Time of the procedure will be recorded.
- ii. Endoscopist survey regarding ease of use and other specifics about the NuView (NASA Task Load Index)

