- 5.5 STEP 5: Gastroscope endoscopic assessment. Using a standard gastroscope, the Olympus GIF-H190, the surgeon will introduce the scope into the patient to assess the esophagus, stomach, and duodenum for polyps. This will be performed per the standard of care without deviation from the current clinical practice during the yearly routine endoscopic examinations for FAP patients.
- 5.6 STEP 6: Endoscopic visualization of the papilla using the NuView (investigational step). Once the surgeon has completed the initial assessment using a gastroscope the NuView device will be attached to the gastroscope and introduced into the patient. The device will be navigated to the duodenum and the papilla will be visualized. Exact sequential protocol for this step is as follows:
  - a. The NuView's sterile packaging will be inspected and confirmed intact.
  - b. The NuView's packaging will be opened.
  - c. The NuView will be attached to the gastroscope and the fitting and attachment will be confirmed to be secure.
  - d. The gastroscope equipped with the NuView will be inserted into the patient in the standard endoscopic fashion.
  - e. The gastroscope will be navigated to the duodenum and the papilla will be visualized using the NuView.
  - f. The gastroscope and device will be removed from the patient.

This is the investigational step of the protocol. All subsequent steps will be performed per the standard of care as they are usually performed for routine endoscopic FAP examinations.

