- 5.7 STEP 7: Confirmation using a standard duodenoscope.** The surgeon will then confirm papilla visualization using a secondary method which is clinically accepted. This will be achieved by inserting a standard duodenoscope, the Olympus TJF-Q180V, to visualize the papilla. This will ensure that anything not visualized with the NuView will be seen using a standard clinically accepted method. Further anything that was visualized by the NuView will again be visualized using a second clinically-accepted standard method. The insertion and assessment with the Duodenoscope will be performed per the standard of care, using the standard protocol for FAP patients during routine yearly endoscopic examinations. The surgeon will insert a duodenoscope into the patient and navigate to the duodenum. The papilla will be inspected to confirm what was visualized using the NuView device. This is a protection in line with what is outlined in 21 CFR 812, which states that any diagnostic NSR device must have a confirmation of diagnosis using a second clinically accepted method. Once the papilla has been visualized using the duodenoscope, the scope will be removed from the patient in the standard clinical method.
- 5.8 STEP 8: Review of adverse events.** In line with standard clinical practice, patients will be closely monitored during the procedure and in a recovery-room setting following the procedure. All available clinical data, including exam findings, and clinical impressions, will be monitored. The investigator will evaluate any changes in physical status and will determine if the change is clinically important and different from what is anticipated in the course of treatment. Similarly, the investigator and sub-investigators will assess on a routine basis if any adverse events occur during the study at any point. All adverse events/complications that occur during the study whether device related or not will be reported and recorded.
- 5.9 STEP 9: Post-endoscopy surgeon NASA index / questionnaire.** Following the procedure, a short NASA task load index / questionnaire will be given to the surgeon to explore various items of interest related to the useability of the device such as mental demand, physical demand, effort, frustration, etc. (Appendix D)

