**Visualization Quality**

How would you rate the quality of the papilla visualization when using the NuView device? Were you able to clearly and comprehensively visualize the papilla? Was the visualization quality negatively impacted by debris or occlusion?

				
Very Poor	Poor	Moderate	Good	Very Good

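### The protocol has no step to record the NuView result before the duodenoscope goes in, and it places the visualization and illumination ratings after it

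*Protocol*

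**What the plan says.** The primary endpoint (section 3.1.3.2) reads: "The primary study endpoint will be successful visualization of the papilla with a standard gastroscope equipped with the NuView platform". No criterion, assessor or time of recording is attached to it. On sample size, section 3.1.6.1 says: "We anticipate enrolling 3 patients to complete the study".

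Section 3.1.6.2 b) sets out the NuView step as six ordered sub-steps, from checking the packaging to the last: "The gastroscope equipped with a NuView will be removed from the patient". Section 5.6 repeats the list as a to f and ends in the same way: "The gastroscope and device will be removed from the patient". Section 3.1.6.2 c) and section 5.7 then have the duodenoscope passed in the same session, where "they will inspect the papilla to confirm what was visualized using the NuView device". No separate operator or reader is named for either pass.

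Section 5.9 (Step 9) places the questionnaire after this: "Following the procedure, a short NASA task load index / questionnaire will be given to the surgeon". Section 3.1.3.2 also has it completed after the procedure, and Table 2 marks it under Follow up. Appendix D shows that this form carries the visualization-quality item, which asks "Were you able to clearly and comprehensively visualize the papilla", and a matching item on illumination.

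**The concern.** The order of the two examinations is sound, because NuView is tried before the better-established view is available. That protects the result only if the NuView result is fixed at that point. If it is declared or graded later, an equivocal structure seen in the mirror can be reinterpreted as the papilla once the duodenoscope has shown where it lies and what it looks like. The quality rating likewise becomes a recollection set against a second image, when it is meant to rate NuView alone.

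This is separate from how success is defined. A precise definition is still exposed to hindsight if it is applied after the reference view. What is at stake is how far the only primary result of a three-patient study can be read as something NuView achieved unaided.

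**Working it through.** **Order of events, from the protocol**

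| Event | Where | Timing relative to duodenoscope |
|---|---|---|
| NuView pass and removal | 3.1.6.2 b), 5.6 | before |
| Recording of the NuView result or image | no step in either list | not stated |
| Duodenoscope inspection | 3.1.6.2 c), 5.7 (Step 7) | – |
| Questionnaire, with visualization and illumination items | 3.1.3.2, 5.9 (Step 9), Table 2 Follow up column, Appendix D | after |

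The two halves differ in strength. For the two quality items the late timing is explicit and agrees across three places. For the success call the protocol is silent: no step records it before the duodenoscope, and none says it is recorded afterwards. Sections 3.3 and 11 mention database entry and case report forms but set no time for this result.

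**Size at n = 3.** The protocol gives no target rate, threshold or power, so there is no figure of its own to reproduce.

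- One changed call shifts the proportion by 1/3, or 33 percentage points: 2/3 = 67% becomes 3/3 = 100%.
- Exact (Clopper-Pearson) 95% interval for 3/3: lower limit 0.025^(1/3) = 0.292, so 29.2% to 100%.
- Exact interval for 2/3: the lower limit solves 3p²(1−p) + p³ = 0.025, giving p = 0.094; the upper limit solves 1 − p³ = 0.025, giving p = 0.992. So 9.4% to 99.2%.

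**Illustration under assumed values.** Let p be the true NuView success rate and f the share of true failures called successes after the reference view. Neither is in the protocol. The chance that a patient is called a success is q = p + (1−p)f, and the chance of a perfect result is q³.

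| p | f = 0 | f = 0.25 | f = 0.50 |
|---|---|---|---|
| 0.5 | 0.500³ = 0.13 | 0.625³ = 0.24 | 0.750³ = 0.42 |
| 0.7 | 0.700³ = 0.34 | 0.775³ = 0.47 | 0.850³ = 0.61 |
| 0.9 | 0.900³ = 0.73 | 0.925³ = 0.79 | 0.950³ = 0.86 |

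The effect is large when the device often fails and modest when it nearly always works.

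**The case against.** A reader might infer that the success call is made after the duodenoscope. The document does not support that. Section 1 has the NuView scope withdrawn once the papilla has been seen, which implies a judgement by the operator at the time, and section 3.1.6.2 c) presupposes an observation already made. What is missing is an instruction to write that judgement down.

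Nor does section 3.1.6.3 show late scoring. It lists "Primary Endpoint: Successful visualization of the papilla with a standard gastroscope equipped with NuView" under the follow-up heading, but the same list restates all the endpoints, including procedure time, which cannot be measured at a follow-up call. Table 2 already puts the NuView step in the Endoscopic Examination column.

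It would also go too far to say that an agreement analysis is compromised. The protocol describes the duodenoscope as a secondary confirmation and a patient protection, and it plans no agreement or accuracy analysis.

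Three further points are fair. The quality items are not the primary endpoint. The 33-point shift would follow from any changed call at this sample size and is not evidence that a change will occur. A locked entry would still be the operator's own unblinded call.

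These points narrow the concern without removing it. The late timing of the quality ratings is explicit, and an unrecorded real-time judgement can still drift. A form not shown here might capture the call early, but the protocol does not require it to. When an outcome is recorded is a matter of study conduct, and an analysis plan cannot recover an observation that was not fixed at the time.

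**Conclusion.** The point holds in a limited form. The visualization and illumination ratings are, as written, given after the reference view in all 3 patients. The primary success call has no stated recording time and no step that fixes it before the duodenoscope, so it is open to the same hindsight. Whether it would in fact be altered cannot be known from the protocol.

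If one equivocal view were reclassified, the primary result would move from 2/3 to 3/3. This rests on the same endoscopist performing both passes, which the text implies but does not say outright, and on no unseen form already locking the call. Patient safety and the order of examinations are not in question. This is an inexpensive improvement to how the result can be interpreted.

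**What to change.** Add one step to section 3.1.6.2 b) and to section 5.6, to be completed before the duodenoscope is inserted:

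- the endoscopist declares the papilla seen or not seen with NuView;
- a still or short clip is saved while the NuView image is on screen;
- study staff enter the call and the clock time, and the entry is not changed afterwards;
- the endoscopist rates the visualization and illumination items.

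Enter confirmation or disagreement by duodenoscope as a separate item. Add a row for recording the NuView result under Endoscopic Examination in Table 2. Leave the rest of the NASA-TLX form after the procedure, and leave the duodenoscope step as it is.

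The cost is a short pause, one extra form line and an image capture. The result may look slightly less favourable. Section 3.1.3.2 already has research personnel recording procedure time; that they are in the room and can take this entry is an inference the sponsor should confirm.
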